8.2.3.4.1 Hematological parameters

The worst value of each hematological category will be identified and graded for each patient. Frequencies and percentages of each category will be tabulated per arm. A table with grade 3/4 frequencies and percentages will be provided.

8.2.3.4.2 Biochemical parameters

The worst value of each biochemical category will be identified and graded for each patient. Frequencies and percentages of each category will be tabulated. A table with grade 3/4 frequencies and percentages will be provided.

8.2.3.4.3 All AEs

The worst grade of each AE item will be identified for each patient. Frequencies and percentages of each CTCAE term will be tabulated grouped by SOC. Tables with all grades and grade 3/4 frequencies and percentages will be provided.

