5.4 Treatment duration

Treatment should be administered until one of the withdrawal criteria has been met (see section 5.5). There is no pre-defined limit to the number of cycles to be administered.

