7.2 Evaluation of safety

7.2.1 Adverse events

All adverse events will be recorded; the investigator will assess whether those events are drug related (reasonable possibility, no reasonable possibility) and this assessment will be recorded in the database for all adverse events.

Only the worst grade per CTCAE category will be recorded per cycle. The collection period will start from randomization up to 30 days after administration of the last dose of protocol treatment or until the start of a new antitumor therapy, whichever occurs first.

All adverse events must be followed until resolution or stabilization.

Whenever possible, the Investigator will record the main diagnosis instead of the signs and symptoms normally included in the diagnoses.

Investigators must pursue and obtain information adequate both to determine the outcome and to assess whether it meets the criteria for classification as a SAE requiring immediate notification.

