8.1 Statistical design

8.1.1 Sample size

This trial is a phase II with a Korn superiority design comparing PFS between trabectedin and control with a treatment allocation ratio equal to 2:1 at randomization. Based on RANO recommendation (Ref. 1), PFS-6=15% was assumed in the control arm and 35% in the trabectedin arm (i.e. 20% difference). Assuming PFS follows an exponential distribution, this corresponds to a treatment Hazard Ratio (HR) equal to 0.55. Based on the logrank test, a type I error equal to 10% one-sided (20% two sided), a power equal to 85%, 72 progressions or deaths are needed to assess the targeted effect. 86 eligible patients who started their treatment (per protocol population) should be recruited (57 trabectedin, 29 control). Assuming 7.17 patients per month (1.99 months 0-4, 3.55 months 4-8, 5.29 months 8-12 and 7.17 beyond 12 months), about 18 months of recruitment are needed. Events should be observed shortly (about 3-4 months) after end of accrual.

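### AE tables give only crude worst-grade percentages over observation times that can differ by arm, so they cannot by themselves separate toxicity from length of observation

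*Combined protocol and SAP*

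**What the plan says.** Section 8.2.3.4.3 (All AEs) states: "The worst grade of each AE item will be identified for each patient". The result is shown as frequencies and percentages by CTCAE term. Sections 8.2.3.4.4 (SAEs) and 8.2.3.4.5 (Related AEs) use the same summary.

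Three other places set the time over which that worst grade is taken:

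- Section 7.2.1 collects AEs from randomization "up to 30 days after administration of the last dose of protocol treatment or until the start of a new antitumor therapy", whichever is earlier.
- Section 8.2.3.4 covers the whole study duration, but uses forms only up to the last safety assessment before progression or further antitumor treatment.
- Section 5.4 says of treatment: "There is no pre-defined limit to the number of cycles to be administered". Section 5.5 ends it at progression, or for toxicity, refusal, investigator decision and other reasons.

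Section 8.2.3.4 also rules out any formal safety comparison, p-value or confidence interval. It specifies no summary of exposure or observation time by arm, no time-at-risk rate, no time-to-first-event analysis and no fixed-window table. Section 7.2.2 has the worst grade per cycle computed for analysis, but no per-cycle table follows from it. Section 8.2.4 plans no sensitivity analysis.

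**The concern.** How long a patient is watched for AEs depends largely on when the disease progresses, which is the primary endpoint. The trial is designed on the assumption that this happens later on trabectedin. For any event that keeps occurring, the chance of at least one episode rises with time watched. A difference between two crude percentages can then reflect toxicity, length of observation, or both, and the planned tables give no means of telling which.

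What is at stake is how a secondary endpoint is read. No test is affected. Section 10 says that a PFS advantage would have to be weighed against the burden of treatment. That weighing is harder if a longer PFS can itself raise the apparent burden, or if early stopping for toxicity can hide it.

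**Working it through.** **Inputs from section 8.1.1.** The share free of progression at 6 months is set at 15% for control and 35% for trabectedin. On the hazard ratio the section says: "Assuming PFS follows an exponential distribution, this corresponds to a treatment Hazard Ratio (HR) equal to 0.55". Allocation is 2:1, with 57 trabectedin and 29 control patients. Accrual follows the stated monthly rates, and the events are expected about 3 to 4 months after accrual ends.

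**Assumption.** The documents give no AE rates. I take an equal constant rate r per month in both arms, so the sizes below are illustrative.

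**1. The plan's own figures.** HR = ln 0.35 / ln 0.15 = 0.553, as stated after rounding. Events by Schoenfeld's formula = (1.282 + 1.036)² / [(2/9) × (ln 0.553)²] = 5.37 / 0.0778 ≈ 69.1, so 70 against the stated 72. Allowing for the futility stop at 36 events (observed HR of 1 or more), 72 events give 84.7% power at HR 0.553 and 85.2% at 0.55. The design inputs are therefore understood correctly.

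**2. Time to progression.** Hazard h = −ln(PFS-6)/6.
- Control: 1.897/6 = 0.316 per month, mean 1/h = 3.2 months.
- Trabectedin: 1.050/6 = 0.175 per month, mean 5.7 months.
- Ratio 1.81.

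**3. Crude percentage at equal AE rates, observed to progression.** Share with at least one event = r/(r + h).

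| r per month | Control | Trabectedin | Gap (points) |
|---|---|---|---|
| 0.017 | 5% | 8.7% | 3.7 |
| 0.035 | 10% | 16.7% | 6.7 |
| 0.079 | 20% | 31.1% | 11.1 |
| 0.136 | 30% | 43.7% | 13.7 |
| 0.211 | 40% | 54.6% | 14.6 |
| 0.316 | 50% | 64.4% | 14.4 |

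In the 20% row the expected counts are 29 × 0.20 = 5.8 and 57 × 0.311 = 17.7. With binomial counts, trabectedin shows the higher percentage with probability about 0.88, although the rates are equal.

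**4. The 20% case under other conditions** (r reset to give 20% on control where the change also affects that arm).

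| Condition | Trabectedin |
|---|---|
| Planned accrual, data cut 3 to 4 months later (mean observation about 2.9 vs 4.4 to 4.6 months) | 28.4% to 28.9% |
| 30 days added after progression in both arms | 28.8% |
| Extra stopping in both arms, 0.05 to 0.20 per month | 28.9% down to 25.6% |
| Extra stopping on trabectedin only, 0.14 per month (mean 3.2 months) | 20.1% |
| Extra stopping on trabectedin only, 0.20 per month | 17.4% |
| All AE risk in cycle 1 | 20.9% |
| HR = 1 | 20% |

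**5. Do the alternatives behave better?**
- *First events per patient-month, constant rate:* 7.9 per 100 patient-months in each arm, ratio 1.0.
- *The same measure when all risk falls in cycle 1 and is identical by arm:* 20.0% of controls over a mean of 2.53 months at risk is 7.9 per 100 patient-months. On trabectedin, 20.9% over 4.52 months is 4.6. The ratio is 0.59, so the longer-observed arm looks safer with no difference in toxicity.
- *Nine-week window (2.07 months), constant r = 0.079:* share = r/(r + h) × [1 − exp(−(r + h) × 2.07)], which gives 11.2% control and 12.7% trabectedin. The gap falls from 11.1 points to 1.5.
- *Cumulative incidence with progression or death as competing event:* read at nine weeks, it gives the same 11.2% and 12.7%. Its plateau is r/(r + h), the crude percentage again, so it helps only if read at a common early time.

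**The case against.** A reader might infer that success on PFS by itself will make trabectedin look more toxic. The documents do not support that. It requires the PFS alternative to be true, AE risk to continue at a steady rate, and patients to stop almost only at progression. Section 5.5 lists other reasons for stopping, and sections 5.6.1.1 to 5.6.1.3 add discontinuation rules specific to trabectedin, so its observation time could be shorter than PFS suggests. Laboratory checks in that arm are weekly only in the first two cycles, which fits early onset for some toxicities, and early events are barely affected. All of this stands. The net direction cannot be known in advance.

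It is also fair that crude incidence is a valid description of total burden under the regimen as delivered, that no formal safety comparison is planned, and that section 2.1 ties the phase III decision to antitumor activity without naming AE percentages. These points limit the consequence. They do not remove the need to show how long each arm was observed, because side-by-side percentages are the main safety summary planned and nothing beside them tells the reader which situation applies.

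Another tempting step is to replace the crude tables with patient-month rates. The cycle-1 example shows that these can mislead in the opposite direction.

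**Conclusion.** The point holds in a conditional form. The planned AE, SAE and related-AE tables do not describe the arms over equal time, and taken alone they cannot separate toxicity from length of observation. With PFS-6 of 15% and 35%, an equal constant AE rate and similar stopping for other reasons, a 20% event on control appears as about 31% on trabectedin, or 28% to 29% under the planned accrual and data cut. For control percentages of 5% to 50%, observed to progression, the spurious gap is about 4 to 15 points. It is zero at HR = 1, under 1 point for cycle-1 events, and gone or reversed once extra stopping on trabectedin reaches about 0.14 per month. The AE rates are assumed, so the sizes are illustrative. The primary analysis is unaffected. This should be changed, as a modest improvement in reporting.

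**What to change.** Keep the crude tables. In 8.2.3.4.3 to 8.2.3.4.5 add, per arm:

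1. A summary of treatment exposure and of AE observation time.
2. As the main basis for side-by-side description, either worst-grade tables over a common early window from first dose (for example about 9 weeks), or cumulative incidence of first event with progression and death as competing events, read at a stated common early time.
3. First-event rates per 100 patient-months as supportive only, with a note that they favour the longer-observed arm when events occur early.

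State how cycle-level records map to the window. Section 7.2.1 records only the worst grade per cycle, section 6 allows 3- or 4-week cycles on control, and section 4 defines control cycles by the chosen drug. Nine weeks is three 3-week cycles but 2.25 four-week cycles.

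Reconcile the AE cut-offs in 7.2.1 (30 days after the last dose or new therapy) and 8.2.3.4 (progression or further therapy), so that each table has one defined end of observation.

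The cost is SAP wording and a few extra tables, with no change in sample size. The documents do not say whether AE onset dates are collected. If they are not, the window is only as precise as the cycle records, and cumulative incidence would have to be by cycle.

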7.2.2 General evaluation of adverse events

This study will use the International Common Terminology Criteria for Adverse Events (CTCAE), version 4.0, for adverse event reporting. A copy of the CTCAE can be accessed from the EORTC home page www.eortc.org/investigators-area/ctc.

The highest CTCAE grading per cycle and per patient will be computed at the EORTC HQ for analysis.

Planned safety analysis and tabulations are described in the statistics section.

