7.2.4 Toxic deaths

Toxic death is defined as death due to toxicity (defined as adverse events at least with reasonable possibility related to study treatment). The cause of death must be reported as "toxicity".

The evaluation of toxic deaths is independent of the evaluation of response (patients can die from toxicity after a complete assessment of the response to therapy).

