8.2.3.4.4 SAEs

After reconciliation with the SAEs listing extracted from the pharmacovigilance database, the worst grade of each serious AE item will be identified for each patient. Frequencies and percentages of each SOC and PT will be tabulated. Tables with all grades and grade 3/4 frequencies and percentages will be provided.

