8.2.3.4.5 Related AEs

The worst grade of each related AE item will be identified for each patient. Frequencies and percentages of each CTCAE term will be tabulated grouped by SOC. Tables with all grades and grade 3/4 frequencies and percentages will be provided.

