Death, as such, is the outcome of a SAE and should not be reported as the SAE term itself. Instead the cause of death should be recorded as the SAE term. When available, the autopsy report or its main conclusions in English will be provided to the Sponsor.

SAR: A Serious Adverse Reaction is defined as any SAE which is considered related to the protocol treatment.

SUSAR: Suspected Unexpected Serious Adverse Reaction.

SUSARs occurring in clinical investigations qualify for expedited reporting to the appropriate Regulatory Authorities within the following timeframes:

- ◆ Fatal or life-threatening SUSARs within 7 calendar days
- ◆ Non-fatal or non-life-threatening SUSARs within 15 calendar days

Inpatient hospitalization: a hospital stay equal to, or greater than, 24 hours.

Prolongation of hospitalization is defined as any extension of an inpatient hospitalization beyond the stay anticipated/required for the initial admission, as determined by the Investigator or the treating physician.

Second primary malignancy is one unrelated to the treatment of a previous malignancy (and is NOT a metastasis from the previous malignancy).

Secondary malignancy is a cancer caused by treatment for a previous malignancy (e.g., treatment with investigational agent/intervention, radiation or chemotherapy). A secondary malignancy is not considered a metastasis of the previous malignancy.

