15.3 Severity assessment

The severity of all AEs (serious and non-serious) in this trial should be graded using CTCAE v4.0
[www.eortc.org\investigators-area\ctc](http://www.eortc.org/investigators-area/ctc)

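### The only high-grade adverse event tables stop at grade 4, so a patient with a fatal event is not counted for that item in them

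*Combined protocol and SAP*

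**What the plan says.** The combined protocol and SAP uses the same two-step rule in three places.

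- **All AEs (8.2.3.4.3):** "The worst grade of each AE item will be identified for each patient". The output is then "Tables with all grades and grade 3/4 frequencies and percentages will be provided".
- **SAEs (8.2.3.4.4):** after reconciliation with the pharmacovigilance database, "the worst grade of each serious AE item will be identified for each patient". The same pair of tables follows.
- **Related AEs (8.2.3.4.5):** "The worst grade of each related AE item will be identified for each patient". Again the same pair of tables follows.

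Four other places bear on how a fatal event passes through this rule.

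- **Grading (15.3):** "The severity of all AEs (serious and non-serious) in this trial should be graded using CTCAE v4.0".
- **Recording of deaths (15.1):** death is an outcome and not an event term. "Instead the cause of death should be recorded as the SAE term".
- **Toxic deaths (7.2.4):** "Toxic death is defined as death due to toxicity". Here toxicity means adverse events with at least a reasonable possibility of relation to study treatment.
- **Where tables are specified (7.2.2):** "Planned safety analysis and tabulations are described in the statistics section". Section 8.2.3.4 is therefore the place to look for any table of fatal events.

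**The concern.** A high-grade table should not show a lower count because an outcome got worse. Under this rule it can. A patient whose event peaks at grade 4 is counted for that item. If the same event goes on to be fatal, the worst grade is no longer 3 or 4, and the patient leaves the count for that item.

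Safety is a named secondary endpoint (2.2). Section 8.2.3.4 rules out formal comparison, p-values and confidence intervals for safety, so the descriptive tables are the whole of the between-arm safety evidence. A reader who takes the grade 3/4 table as the summary of high-grade toxicity would see too low a rate for any item with fatal cases.

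**Working it through.** There is no stated figure in the plan to reproduce. The check traces the rule and then computes simple proportions.

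**Step 1: how a fatal event is graded.** Section 15.1 places the death under the term for its cause, and 15.3 grades that term by CTCAE v4.0. On that scale a fatal AE has grade 5. The documents never write grade 5, so this is the one assumption drawn from the scale itself.

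**Step 2: how the patient is classified.** Sections 8.2.3.4.3 to 8.2.3.4.5 keep one grade per patient per item, the worst. For the fatal item that grade is 5.

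**Step 3: which tables count the patient.**

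| Table | Fatal item | Other items of the same patient, worst grade 3 or 4 |
|---|---|---|
| All grades | counted | counted |
| Grade 3/4 | not counted | counted |

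**Step 4: does another planned table restore the count?** Section 8.2.3.4 plans no table of grade 3 or higher, of grade 5, or of toxic deaths. The definition in 7.2.4 is not attached to any summary. Section 8.2.3.4 does plan a listing of severe grades that persist after treatment stops or first appear in follow-up. A listing does not alter the percentages in the tables.

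**Step 5: size per case.** The inputs are the planned arm sizes in 8.1.1, 57 trabectedin and 29 control. These are per-protocol targets. The safety population in 8.2.2 also includes ineligible patients who started treatment, so they are an approximation. The shift per fatal case is 1/n:

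- trabectedin: 1/57 = 1.75 points
- control: 1/29 = 3.45 points

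**Step 6: illustration.** The counts are assumed and do not come from the documents. Let g be the patients with worst grade 3 or 4 for an item, and f those with a fatal event for it. The planned table shows g/n; a table of grade 3 or higher shows (g + f)/n.

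| Arm | g/n, as planned | f = 1 | f = 2 | f = 3 |
|---|---|---|---|---|
| Trabectedin, 10/57 | 17.5% | 19.3% | 21.1% | 22.8% |
| Control, 5/29 | 17.2% | 20.7% | 24.1% | 27.6% |

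With f = 0 the two tables agree.

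**Step 7: laboratory tables.** Sections 8.2.3.4.1 and 8.2.3.4.2 also plan grade 3/4 tables, but these grade the worst laboratory value. The argument in steps 1 to 3 concerns event terms that carry a fatal outcome, so it is not extended to them.

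**The case against.** The best defence is that this is a matter of layout. The grade 3/4 table would correctly count grades 3 and 4, and the plan nowhere calls it the severe-event rate. Fatal cases are in the all-grades table, and if that table has a column per grade, a reader can add up grade 3 or higher. Fatal toxicity also surfaces elsewhere: a toxic death must have toxicity reported as its cause (7.2.4), SAEs are reconciled with the pharmacovigilance database (8.2.3.4.4), an unresolved fatal event plausibly falls in the listing, and monitoring committees review safety (8.3). Under 15.2, events related to the primary cancer or its progression are generally not reported as SAEs, which reduces the fatal cases reaching the SAE table.

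Much of this stands, and it rules out three stronger readings that a reader might infer.

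- **That fatal toxicity would go unreported.** The all-grades tables include it, and the other routes make it unlikely to be missed.
- **That the patient disappears from the high-grade count altogether.** The loss is per item; the patient still counts for other items with worst grade 3 or 4.
- **That the plan biases the safety comparison between arms.** The rule is the same in both arms, no formal comparison rests on it, and the documents give no expected number of fatal AEs. A distortion needs fatal cases that are unevenly spread between arms within an item.

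What does not stand is that the other outputs make the change unnecessary. The text does not say that the all-grades table is broken down by grade, and none of the other routes corrects the high-grade percentages.

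**Conclusion.** The point holds as a minor one. Applied exactly as written, 8.2.3.4.3 to 8.2.3.4.5 leave a fatal item out of the only high-grade table, by about 1.8 points per case with trabectedin and 3.4 points per case with control. This rests on two assumptions: that CTCAE v4.0 gives a fatal AE its own grade above 4, and that 57 and 29 approximate the safety-population arm sizes. The total effect cannot be stated, because the number of fatal AEs is unknown and may be zero. Sample size, power, type I error and the primary analysis are not affected.

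**What to change.** In 8.2.3.4.3, 8.2.3.4.4 and 8.2.3.4.5:

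1. Replace grade 3/4 by grade 3 or higher (3-5).
2. Show grade 5 in its own column.
3. Add the per-arm count of toxic deaths, using the definition in 7.2.4.

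Leave 8.2.3.4.1 and 8.2.3.4.2 as they are. The change touches table shells only; it needs no new data, visits or analysis methods.

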8.2.3.4.4 SAEs

After reconciliation with the SAEs listing extracted from the pharmacovigilance database, the worst grade of each serious AE item will be identified for each patient. Frequencies and percentages of each SOC and PT will be tabulated. Tables with all grades and grade 3/4 frequencies and percentages will be provided.

8.2.3.4.5 Related AEs

The worst grade of each related AE item will be identified for each patient. Frequencies and percentages of each CTCAE term will be tabulated grouped by SOC. Tables with all grades and grade 3/4 frequencies and percentages will be provided.

8.2.4 Pre-planned sensitivity or exploratory analyses

There is no pre-planned sensitivity analysis. Exploratory analyses may be performed on the basis of subgroup of patients (e.g. Ki67 expression, microvascular density, and density of tumor-associated macrophages), but results of these exploratory analyses may not serve as a basis for drawing conclusions concerning protocol treatment efficacy, and the reasons for excluding patients should be clearly reported.

Below a power table. It assumes worse prognosis in a high proliferation subgroup. Different rates of high proliferation and prognostic detrimental effect (HR>1) are computed.

Power to show the prognostic effect of a proliferation index in the whole population with 71 PFS events at 2.5% significance (one-sided).

	Hazard Ratio			
High proliferation rate	HR=1.95	HR=2	HR=2.5	HR=3.05
10%	<80%	41.5%	63.5%	80%
20%	<80%	64.5%	87%	>80%
30%	<80%	76%	94%	>80%
40%	<80%	81.5%	96.5%	>80%
50%	80%	83%	97%	>80%

